### 11. ADVERSE EVENTS

#### 11.1 Definitions

### 11.1.1 Adverse Event

The term "adverse event" (AE) includes any sign, symptom, syndrome, or illness that appears or worsens in a subject during the period of observation in the clinical study and that may impair the wellbeing of the subject. The term also covers laboratory findings or results of other diagnostic procedures that are considered to be clinically significant (*e.g.*, that requires unscheduled diagnostic procedures or treatment measures, or result in withdrawal from the study). An abnormal lab value or test results constitute an adverse event if they are considered clinically significant or require therapy. An AE is therefore any unfavorable and unintended symptom or disease temporally associated with the administration of an investigational product, whether or not related to that investigational product.

The adverse event may be:

- A new illness/condition;
- Worsening of a sign or symptom of the condition under treatment, or of a concomitant illness/condition;
- An effect of the study drug; or
- A combination of 2 or more of these factors.

No causal relationship with the study drug or with the clinical study itself is implied by the use of the term "adverse event."

The Investigator or his/her designee will probe, via discussion with the subject, for the occurrence of AEs during each subject visit and record the information in the site's source documents. AEs will be recorded in the subject CRF. AEs will be described by duration (start and stop dates and times), severity, outcome, treatment and relation to study drug, or if unrelated, the cause.

Surgical procedures themselves are not adverse events; they are therapeutic measures for conditions that require surgery. The condition(s) for which the surgery is required may be an adverse event. Planned surgical measures permitted by the clinical study protocol and the condition(s) leading to these measures are not adverse events.

When a clear diagnosis is available that explains the abnormal objective findings, this diagnosis will be recorded as an adverse event and not the abnormal objective findings (*e.g.*, viral hepatitis will be recorded as the adverse event and not the transaminase elevation). If a definitive diagnosis is

not available, then the sign(s) (e.g., clinically significant elevation of transaminase levels) or symptom(s) (e.g., abdominal pain) will be recorded as the adverse event.

Adverse events fall into the categories "serious" and "non-serious."

#### **11.1.2 Serious Adverse Event**

A serious adverse event is one that at any dose of the study drug or at any time during the period of observation:

- Results in death;
- Is life-threatening (defined as an event in which the subject was at risk of death at the time of the event; it does not refer to an event which hypothetically might have caused death if it were more severe);
- Requires inpatient hospitalization or causes prolongation of existing hospitalization (see note below for exceptions);
- Results in persistent or significant disability/incapacity;
- Is a congenital anomaly/birth defect; or
- Is an important medical event, defined as a medical event that may not be immediately life-threatening or result in death or hospitalization but, based on appropriate medical and scientific judgment, may jeopardize the subject or may require intervention (e.g., medical, surgical) to prevent one of the other serious outcomes listed above. Examples of such events include but are not limited to intensive treatment in an emergency department or at home for allergic bronchospasm; blood dyscrasias or convulsions that do not result in hospitalization. "Medically important" should be marked only if no other serious criteria are met.

An "unexpected SAE" is any SAE for which the nature, specificity or severity is not consistent with the currently known adverse event profile of the investigational agent(s).

**NOTE:** The following hospitalizations are not considered SAEs in UFHCC clinical studies:

- a visit to the emergency room or other hospital department lasting less than 24 hours that does not result in admission (unless considered an "important medical event" or a life-threatening event).
- elective surgery planned before signing consent.
- admissions as per protocol for a planned medical/surgical procedure.
- routine health assessment requiring admission for baseline/trending of health status (e.g., routine colonoscopy).

- medical/surgical admission for purpose other than remedying ill health state that was planned before study entry. Appropriate documentation is required in these cases.
- admission encountered for another life circumstance that carries no bearing on health status and requires no medical/surgical intervention (e.g., lack of housing, economic inadequacy, caregiver respite, family circumstances, administrative).

#### **Clarification of the difference in meaning between “severe” and “serious”**

The term “severe” is often used to describe the intensity (severity) of a specific event (as in mild, moderate, or severe myocardial infarction); the event itself, however, may be of relatively minor medical significance (such as severe headache). Any grade  $\geq 3$  adverse event per CTCAE is generally considered severe AE. This is not the same as “serious,” which is based on the outcome or action criteria usually associated with events that pose a threat to life or functioning. Seriousness (not severity) serves as a guide for defining regulatory reporting obligations.

#### **11.1.3 Non-Serious Adverse Event**

A non-serious adverse event is any adverse event not meeting any of the serious adverse event criteria.

#### **11.2 Period of Observation**

Following the subject’s written consent to participate in the study, all SAEs must be collected, including those thought to be associated with protocol-specified procedures. Collection of all SAEs must continue for **30 days** after the last administration of the investigational product. If applicable, SAEs must be collected that relate to any later protocol-specified procedure (e.g., a follow-up skin biopsy). The investigator should notify the DISC of any SAE occurring after this time period that is believed to be related to the investigational product or protocol-specified procedure.

The investigator will begin collecting non-serious adverse event (NSAE) information once administration of the investigational product is initiated. This NSAE information should also be collected from the start of a placebo lead-in period or other observational period intended to establish a baseline status for the subjects. Treated subjects, including those who were prematurely discontinued from the study, will be followed for any adverse events that occur during the study until 30 days following the last dose of study treatment (i.e., the Follow-up Visit). However, if another course of anti-cancer therapy is initiated prior to the 30-day follow-up

period visit, collection of adverse events will no longer be performed, with the exception of events that may be possibly, probably, or definitely related to the investigational agent or are clinically significant.

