## 6.1 Schedule of Events

Procedure:	Visit:	SCREENING (Windows outlined in Section 6.2)	CYCLE 1	CYCLES 2 AND BEYOND (WITHIN 72 HRS PRIOR)	END OF TREATMENT (WITHIN 14 DAYS OF LAST STUDY DRUG ADMINISTRATION)	FOLLOW UP (28 +/- 7 DAYS AFTER LAST DOSE OF TREATMENT)	SURVIVAL FOLLOW UP EVERY 90 +/- 14 DAYS AFTER LAST DOSE
Informed Consent		X					
Medical History, Demographic Information		X					
Clinical Exam		X	X	X	X		
Performance status (PS) 		X	X	X	X		
Vital Signs (VS) including height  , weight, and BSA 		X	X	X	X		
Numbered Pain Rating Scale 			X	X	X		
Labs (CBC diff, CMP) 		X	WEEKLY 	X			X 
Pregnancy Test (Urine or Serum) 		X	X	X			
INR		X					
Tibial x-ray 		X		X 			
Provide Study Drug for home administration			X	X			
Tumor disease evaluation 		X		EVERY 2 CYCLES 	X		
Tumor NGS 		X					
Circulating tumor DNA (ctDNA) 				X	X		
Provide and/or Review Subject Diary			X	X	X		
Concomitant Medication Review 		X	X	X	X		
Adverse Event Review 			X	X	X	X	
Survival Assessment							X

Abbreviations: VS=vital signs (blood pressure, temperature, pulse and respiratory rates, weight and height); CBC/diff=complete blood count and white blood cell differential; CMP = complete metabolic profile (sodium, potassium, chloride, bicarbonate, blood urea nitrogen, creatinine, glucose, alkaline phosphatase, AST, ALT, total bilirubin, protein), NGS Next Generation Sequencing

1 Performance status: Pediatric Karnofsky for subjects  $\geq$  16 years of age and Lansky for subjects 12-15 years of age; Adult ECOG score (18+)

UF-SC-001

2024-Aug-12

- 2 Numbered Pain Rating Scale , refer to Appendix G.
- 3 Laboratory tests at baseline need not be repeated if therapy starts within 72 hours of obtaining labs to assess eligibility. Labs are to be collected weekly for Cycle 1 (Days 1, 8, 15, and 22) +/- 72 hours. If patients have Grade 4 neutropenia then CBCs should be checked at least every other day until recovery to Grade 3 or until meeting the criteria for dose limiting toxicity. Automated differentials acceptable unless concern for blasts; then please obtain manual differential.
- 4 Female subjects of childbearing potential only.

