## 6.2 Allowable Visit Windows

Visit Name	Window
Screening	
Informed Consent	≤ 28 days prior to Cycle1 Day 1 (C1D1)
Medical History, Physical examination, Performance Status, Concomitant Medications, and Labs (CBC Diff, CMP, INR, pregnancy test)	≤ 28 days prior to Cycle1 Day 1 (C1D1)
Tibial X-Ray	≤ 180 days prior to Cycle1 Day 1 (C1D1)
Imaging (CT and PET)	≤ 30 days prior to Cycle1 Day 1 (C1D1)
All other screening procedures	≤ 7 days prior to C1D1
Cycle 1 Day 1	
Labs	Laboratory tests at screening need not be repeated if therapy starts within 72 hours of obtaining labs to assess eligibility. All others to be done ≤ 72 hours of C1D1 dosing. Labs are to be collected weekly for Cycle 1 (Days 1, 8, 15, and 22) +/- 72 hours
All other baseline procedures (which include complete physical exam, performance status, vital signs, and concomitant medication review)	Baseline procedures completed at screening need not be repeated if therapy starts within 72 hours of performing procedures to assess eligibility. All others to be done ≤ 72 hours of C1D1 dosing.
Day 1 of subsequent cycles (after Cycle 1)	
Assessments	Within 72 hours prior to dosing
Study treatment administration (dosing)	Every 28 days
Tibial X-Ray	Every 180 +/- 30 days
Tumor Assessments	Imaging every 2 cycles +/- 7 days from Cycle 1 Day 1 until disease progression or death.
End of Treatment (EOT) Procedures	Within 14 days of last dose of therapy
28-Day Safety Follow-up	28 +/- 7 days after last dose of treatment

Survival Follow-Up	Every 90 +/- 14 days
--------------------	----------------------

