#### 6.4 Follow up/ Evaluations

Subjects will have a follow-up visit for the evaluation of adverse events 28 days ( $\pm$  7 days) after the last dose of study medication. Any adverse events ongoing at the follow up visit will be followed until resolution or start of a new therapy. If the subject is unavailable to travel to the institution, the visit may be made via telephone interview to review for adverse event resolution or the occurrence of any new adverse events. Additionally, external or internal medical records may be consulted with permission of the subject to complete remote visit reporting.

Subjects will continue to be contacted via telephone for survival approximately every 90 +/- 14 days until death. Safety labs (CBC) will be performed as part of these visits for 5 years, then annually until 10 years (at least once per calendar year) after last dose of therapy. Labs may be collected at an outside laboratory as standard of care. If study therapy is discontinued for reasons other than progression, continue imaging/disease assessments per standard of care until progression or until start of another therapy or death. Following discontinuation of study therapy for any reason, report the date the first non-protocol anti-cancer therapy is administered. Once a subject begins new anti-cancer therapy, the subject will be followed for survival only.

If a subject becomes unreachable during the course of the study, the investigator or study team will make a reasonable effort to contact the subject and document each attempt (in accordance with Section 4.3.4 of the ICH E-6 GCP). If these attempts are not successful, the subject may be declared "lost to follow up." For subjects lost to follow-up, the termination date will be the date of last contact with the subject.

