#### **12.6 Analysis of Safety Data**

The incidence, severity and reversibility of toxicities will be performed on all subjects who receive any dose of study medication. Non-serious adverse events that occur more than 30 days after the administration of the last dose of treatment will not be included. The safety and tolerability of treatment is determined by reported AEs, physical examinations, and laboratory tests.. AEs will be summarized with the incidence and percentage of subjects with at least one occurrence of a preferred term (NCI - CTCAE Version 5 grade) will be included. The number of AEs reported will also be summarized. Causality (relationship to study drug) will be summarized separately. Duration of AE will be determined and included in listings along with action taken and outcome.

Laboratory results will be classified according to NCI-CTCAE, Version 5.0. Incidence of laboratory abnormalities will be summarized; laboratory results not corresponding to an NCI- CTCAE Version 5.0 term will not be graded. Laboratory toxicity shifts from baseline to worst grade will also be provided. The results from physical examination and vital sign measurement will be tabulated.

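### Adverse event follow-up is set at 30 days but tied to a visit allowed from day 21, so new non-serious events can go unsolicited for up to 9 days of the post-treatment period that is analysed

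*Combined protocol and SAP*

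**What the plan says.** Section 11.2 sets the end of adverse event follow-up for treated subjects: "until 30 days following the last dose of study treatment (i.e., the Follow-up Visit". The parenthesis names the Follow-up Visit as the day-30 point.

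Three other places date that visit differently. The schedule of events in Section 6.1 heads the column "FOLLOW UP (28 +/- 7 DAYS AFTER LAST DOSE OF TREATMENT". The window table in Section 6.2 gives "28 +/- 7 days after last dose of treatment". Section 6.4 says "Subjects will have a follow-up visit for the evaluation of adverse events 28 days", with the same 7-day tolerance. In the schedule this is the last column in which adverse event review is marked. Later contacts, about every 90 days, are for survival and a blood count.

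Section 12.6 sets the analysis limit by day and not by visit: "Non-serious adverse events that occur more than 30 days after the administration of the last dose of treatment will not be included".

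Serious events have a separate rule in Section 11.2. "Collection of all SAEs must continue for" 30 days after the last administration, with no mention of a visit. Section 8.2 also works with 30 days for serious events.

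**The concern.** Collection and analysis do not end at the same point. A site that follows the visit schedule can do its last adverse event review on day 21 and regard Section 11.2 as satisfied, because that section says the visit is the end of follow-up. A site that reads the 30 days literally goes on to day 30. Both are keeping to the text.

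Under the first reading, a non-serious event that begins between the visit and day 30 falls inside the Section 12.6 analysis period, but nobody is scheduled to ask about it. Section 11.1.1 has the investigator probe for events at each visit, so where there is no visit there is no planned questioning. What is at stake is the completeness of the safety tables. The primary endpoint, its type I error and its power are not affected.

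**Working it through.** The check is date arithmetic on the windows stated in the plan, with days counted from the last dose.

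**Inputs**
- Follow-up Visit: day 28, tolerance 7 days (Sections 6.1, 6.2, 6.4).
- End of adverse event follow-up: day 30, equated with the visit (Section 11.2).
- Last day on which a non-serious event is counted: day 30 (Section 12.6).
- Survival contacts: every 90 days, tolerance 14 days, no adverse event review marked (Sections 6.1, 6.4).

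**Does day 30 equal the visit?** The permitted range is 28 − 7 = 21 to 28 + 7 = 35, which is 15 possible days. Day 30 is one of them, and it is not the nominal one. The equation in Section 11.2 does not hold in general.

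**Size of the gap.** Days without a scheduled review = max(0, 30 − visit day). Days reviewed beyond the cut-off = max(0, visit day − 30).

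| Visit day | Days to day 30 without scheduled review | Days reviewed past day 30 |
|---|---|---|
| 21 (earliest) | 9 (days 22 to 30) | 0 |
| 28 (nominal) | 2 (days 29 and 30) | 0 |
| 30 | 0 | 0 |
| 35 (latest) | 0 | 5 |

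**Does a later contact close the gap?** The earliest first survival contact is day 90 − 14 = 76, and it carries no adverse event review. Section 6.4 adds only this: "Any adverse events ongoing at the follow up visit will be followed until resolution or start of a new therapy". That covers events already present at the visit and not those that start afterwards.

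**Scale.** Against the 30-day post-treatment tail, the maximum gap is 9/30 = 30% and the nominal gap is 2/30 = 7%. The tail is only the last part of the period analysed, which begins at first dose. With the maximum of 26 cycles the period is 26 × 28 + 30 = 758 days, and 9/758 = 1.2%. For a subject assumed to stop after 2 cycles it is 2 × 28 + 30 = 86 days, and 9/86 = 10.5%. The 2-cycle case is an illustration and not a figure from the plan.

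**Leverage of one missed event.** Section 12.6 reports the percentage of subjects with at least one occurrence of a term. With up to 50 subjects enrolled, one subject is at least 1/50 = 2%.

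**The case against.** The best defence is that the operative words in Section 11.2 are the 30 days, and the parenthesis is loose drafting. A site that reads the duration literally collects through day 30, Section 11.3 requires every adverse event to be recorded, and ongoing events are followed beyond the visit. This stands as far as it goes: loss is possible and not certain, and it is confined to new events that start after an early visit and are not volunteered. It does not remove the inconsistency, because a site that stops at the visit also complies.

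A reader might infer more than the documents support on four points.

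- *That serious events are left uncollected.* Section 11.2 requires their collection for 30 days irrespective of any visit, and beyond that it adds: "The investigator should notify the DISC of any SAE occurring after this time period", where the event is believed related to the product or a protocol procedure. The obligation is clear. What is missing is a scheduled contact to prompt it.
- *That 30% of the safety analysis period is unobserved.* That share applies only to the post-treatment tail, and only for a visit on the earliest permitted day.
- *That a post-treatment event rate is biased.* Section 12.6 plans no such rate. It reports subject incidence among all who received any dose, and with a single arm there is no between-arm contrast to distort.
- *That dropping events from days 31 to 35 is an error.* A fixed cut-off is what stops a late visit from lengthening the period for some subjects.

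Follow-up length also differs between subjects by design, because Section 11.2 ends most collection when new anti-cancer therapy starts before the visit. That is a stated exception with its own rationale, and it should be kept.

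**Conclusion.** The inconsistency is real, and its consequence is small. New non-serious events can go unsolicited for up to 9 days of the 30-day post-treatment tail, and for 2 days if the visit falls on the nominal day 28. The direction is towards slightly understating incidence. The documents do not allow the number of missed events to be estimated, since they give neither the spread of actual visit days nor an event rate after stopping treatment.

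The conclusion assumes that some sites or staff take the visit as the end point, and that subjects do not volunteer every new event afterwards. For serious events only the prompt is absent. This is a cheap improvement to data collection and not a threat to the trial's conclusions.

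**What to change.** 1. In Section 11.2, delete the parenthesis that equates day 30 with the Follow-up Visit, so that the duration alone governs.
2. In Sections 6.1, 6.2 and 6.4, do one of two things: set the safety follow-up visit no earlier than day 30 (for example day 30 with a window of plus 7 days), or keep the present window and require a telephone adverse event check on or after day 30 whenever the visit was earlier. Either brings the unsolicited days from a maximum of 9 to 0, and also supplies the missing prompt for serious events.
3. Keep the Section 11.2 exception for subjects who start new anti-cancer therapy, including its carve-out for related or clinically significant events. Tie it to day 30, because the section now refers to a 30-day visit that is not on the schedule.
4. Make the same correction in Section 7.5.2, where recording of concomitant medication refers to a thirty-day visit.
5. Leave the 30-day cut-off in Section 12.6 as it is, and check that all six sections (6.1, 6.2, 6.4, 7.5.2, 11.2 and 12.6) give the same end point.

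The cost is a wording amendment plus an occasional telephone call or a visit a few days later. Section 6.4 already allows this follow-up to be done by telephone for subjects who cannot travel. No efficacy analysis changes.

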### **11.3 Documenting and Reporting of Adverse Events by Investigator**

All adverse events must be fully recorded in the subject's case record form. Documentation must be supported by an entry in the subject's file. A laboratory test abnormality considered clinically relevant, e.g., causing the subject to withdraw from the study, requiring treatment or causing apparent clinical manifestations, or judged relevant by the investigator, should be reported as an adverse event. Each event should be described in detail along with start and stop dates, severity, relationship to investigational product, action taken and outcome.

Every attempt should be made to describe the adverse event in terms of a diagnosis that encompasses the component signs and symptoms. If only nonspecific signs or symptoms are present, then these should be recorded as separate diagnoses on the pages of the case report form.

All subjects who have adverse events, whether considered associated with the use of study drug or not, must be monitored to determine the outcome. The clinical course of the adverse event will be followed according to accepted standards of medical practice, even after the end of the period of observation, until a satisfactory explanation is found or the Principal Investigator considers it medically justifiable to terminate follow-up. Should the adverse event result in death, a full pathologist's report should be supplied, if possible.

#### **11.3.1 Assessment of Causal Relationship of Study Drug**

The Investigator will provide an assessment of the potential causal relationship between adverse events and study medication by determining whether or not there is a reasonable possibility that the event was caused by the study medication. The relationship or association of the adverse event to the study medication will be characterized as not related, unlikely related, possibly related, probably related, or related:

**Not Related:** There is not a temporal relationship to the study drug administration or the adverse event is clearly due only to the progression of the underlying disease state, intercurrent illness, concomitant medication, concurrent therapy or other known cause.

**Unlikely Related:** There is little or no chance that the study drug

administration caused the adverse event; the event is most likely due to another competing cause, including intercurrent illness, progression or expression of the disease state, or a reaction to a concomitant medication or concurrent therapy appearing to explain the reported adverse event.

**Possibly Related:** The association of the adverse event with the study drug administration is unknown; however, the adverse event is not reasonably attributed to any other condition.

**Probably Related:** When a reasonable temporal relationship exists between the adverse event and the study drug administration; significant symptoms abate upon discontinuation of the study drug and there is a reasonable explanation based on known characteristics of the study drug and there is no clear association with preexisting disease or therapy, intercurrent illness, concurrent therapy or other factor(s).

**Related:** When the adverse event is a known side effect of the study drug or there is a temporal relationship to the administration of the study drug; or the adverse event reappears upon re-administration of the study drug (rechallenge); or the significant symptoms of the adverse event abate upon discontinuation of the study drug (dechallenge).

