### 7.6.1 Non- Hematologic Toxicity

Non- Hematological dose limiting toxicity is defined as any Grade 3 or greater non-hematological toxicity attributable to the investigational drug with the specific exclusion of:

- Grade 3 nausea and vomiting of less < 3 days duration.
- Grade 3 liver enzyme elevation, including ALT/AST/GGT that returns to levels that meet initial eligibility criteria or baseline within 7 days.
- Grade 3 or 4 fever < 5 days duration.
- Grade 3 infection < 5 days duration.
- Grade 3 hypophosphatemia, hypokalemia, hypocalcemia or hypomagnesemia responsive to supplementation.
- Any Grade 2 non-hematological toxicity that persists for  $\geq 7$  days and is considered sufficiently medically significant or sufficiently intolerable by patients that it requires treatment interruption.
- **Note:** Allergic reactions that necessitate discontinuation of study drug will not be considered a dose-limiting toxicity.

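### The causality categories in 11.3.1 are neither ordered nor mutually exclusive, so an event that either drug or disease could explain is generally pushed into Related

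*Combined protocol and SAP*

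**What the plan says.** Section 11.3.1 asks the investigator to assess causality by "determining whether or not there is a reasonable possibility that the event was caused by the study medication". The relationship is then "characterized as not related, unlikely related, possibly related, probably related, or related".

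The definitions that matter here are these:

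- **Not Related** needs either no temporal relationship or that "the adverse event is clearly due only to the progression of the underlying disease state", or to another listed cause.
- **Unlikely Related** begins "There is little or no chance that the study drug" and goes on to require that a competing cause be the most likely one.
- **Possibly Related** says that the association is unknown, but that "the adverse event is not reasonably attributed to any other condition".
- **Probably Related** joins its criteria with 'and': a reasonable temporal relationship, abatement on stopping, an explanation from known drug characteristics, and no clear association with disease, other therapy or another factor.
- **Related** joins its criteria with 'or': a known side effect, a temporal relationship, recurrence on rechallenge, or abatement on dechallenge.

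Three other sections use attribution. Section 12.6 says "Causality (relationship to study drug) will be summarized separately". Section 11.2 ends adverse event collection once new anti-cancer therapy starts before the 30-day visit, "with the exception of events that may be possibly, probably, or definitely related to the investigational agent or are clinically significant". Section 7.6.1 defines non-hematological dose-limiting toxicity as "any Grade 3 or greater non-hematological toxicity attributable to the investigational drug", subject to listed exclusions.

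**The concern.** In advanced MPNST many adverse events will have two candidate causes. Section 10.1.7 lists pain, fatigue and nausea among the most common reactions to the drug, and the tumor can plausibly produce them too. A causality scale exists largely to place such events. The natural place is the middle category, and the section's own opening test, a reasonable possibility of drug causation, points there. The definition of Possibly Related shuts them out.

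The trial is single-arm, so it has no control group against which to set the background rate of these symptoms. Investigator attribution is its only internal means of separating drug toxicity from disease. If the categories do not mean what their names suggest, the causality table in 12.6 cannot be read at face value, and two investigators may code the same event at opposite ends of the scale.

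**Working it through.** No sample size, error rate or event rate enters this point, so there is no figure in the plan to reproduce. The check applies each definition literally to a test event, compares the definitions with one another, and follows the event through the sections that use causality.

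**Test event.** Fatigue that begins after dosing in a subject with advanced MPNST, with drug and disease equally plausible. Two facts are taken as given: the event follows dosing, and fatigue is a listed reaction (10.1.7). That the tumor can also cause fatigue is a clinical assumption.

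1. Not Related: fails. There is a temporal relationship, and the event is not clearly due to disease alone.
2. Unlikely: fails. The chance of a drug cause is more than minimal, and no competing cause is the most likely one.
3. Possibly: fails. Disease is a reasonable attribution.
4. Probably: normally fails. It could be met only if the symptom abates on stopping and the association with disease is judged not to be clear. Hence 'generally none' of the four lower categories, not 'none'.
5. Related: met twice, as a known side effect and through the temporal relationship.

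**Order.** In an ordered scale each step up should demand at least as much as the step below.

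- On alternative causes, Possibly bars a reasonable attribution to another condition, Probably bars a clear association, and Related bars nothing.
- On timing, Probably needs a reasonable temporal relationship plus three further criteria. For Related, a temporal relationship alone is enough.
- On dechallenge, abatement is one of several necessary conditions for Probably and a sufficient condition for Related.

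The top category is therefore looser than the one beneath it.

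**Exclusivity.** Every event that meets Probably has a temporal relationship, so it also meets Related. An event with a temporal relationship that is most likely due to an intercurrent illness can meet both Unlikely and Related. The categories overlap, and 11.3.1 gives no rule for choosing between them.

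**Where the event goes next.**

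- 12.6: it is counted in the overall adverse event tables whatever its code, and it enters the causality summary as Related, or as Unlikely if the investigator departs from the text. The section does not say which categories make up drug-related events.
- 11.2: the scale's nearest counterpart of definitely related is Related, but the two labels are not equated anywhere.
- 7.6.1: 'attributable' is not tied to any category in 11.3.1.

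**The case against.** The strongest reply is that no event is left without a category. On the text as it stands, an event with a temporal relationship always qualifies as Related, and one without it qualifies as Not Related. That is correct. It limits the point to misclassification, but it does not remove it: the event reaches a category only because the highest one is the loosest.

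Three stronger readings are tempting, and the documents do not support them.

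- A reader might infer that mixed-cause events will be under-reported as drug-related. That requires investigators to choose Unlikely against its wording. The literal text sends these events upward, so the predictable error is over-attribution. Any percentage for a downward bias would rest on assumed inputs.
- A reader might infer that such events drop out of the data. Section 11.2 is the only one of these rules that names possibly related, and it also keeps probably and definitely related events and anything clinically significant. Serious events are collected to 30 days after the last dose whatever their cause, and 12.6 does not filter the safety data by causality. Loss would need a non-serious, not clinically significant event, coded downward, arising after new therapy that began before the 30-day visit.
- A reader might infer that a new anti-cancer therapy makes Possibly unattainable under 11.2. Possibly refers to another condition, while Not Related, Unlikely and Probably name therapy separately. A new drug is not plainly a condition.

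**Conclusion.** The point holds as a defect in the definitions. Possibly Related is too strict, Related is looser than Probably Related, and the categories overlap with no tie-break rule. An event that drug or disease could explain generally bypasses the four lower categories and is coded Related. The causality summary in 12.6 is distorted upward on the literal reading, and it depends on the coder where an investigator resists that reading. The label definitely related in 11.2 has no match in 11.3.1.

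The documents give no frequency of mixed-cause events and no data on how investigators code them, so the size of the distortion cannot be stated. The conclusion rests on reading the definitions as written and on the assumption that events such as fatigue, nausea and pain can arise from the tumor as well as the drug. It does not touch the objective response rate, type I error, power, sample size or overall adverse event incidence. It should be corrected because attribution carries unusual weight in a single-arm trial and the correction is cheap.

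**What to change.** Change the definitions together, because correcting only one leaves a gap or an overlap.

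- 11.3.1, Possibly Related: a reasonable temporal relationship exists and the study drug could have caused the event, but underlying disease, intercurrent illness or other therapy could also explain it.
- 11.3.1, Related: make it stricter than Probably, so that neither a temporal relationship alone nor known-side-effect status alone is enough.
- 11.2: replace definitely related with the labels of the 11.3.1 scale.
- 12.6: state which categories count as drug-related in the causality summary.
- 7.6.1: the sponsor should reconcile 'attributable' with the 11.3.1 scale. Which categories should meet that term is a clinical decision, and no answer is proposed here.

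The cost is protocol and CRF-guideline wording, plus a re-review of causality codes already entered so that all subjects are graded on the same definitions.
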